#### **5.1.5 Pulse Wave Velocity (PWV) and Pulse Wave Analysis (PWA)**

Pulse Wave Velocity (PWV) and Pulse Wave Analysis (PWA) will be performed in the by a trained professional. . Aortic PWV measurements are performed in the supine position after at least 5 minutes rest using the right carotid and right femoral arteries, with a Sphygmocor PVx System (AtCor Medical, West Ryde, Australia) device. PWA will provide novel, supplemental data about central pulse pressure (CPP) in our subjects. The same software and equipment as for PWV are used, on the right radial artery. CPP is measured using radial artery tonometry.

#### **5.1.6 Anthropometry**

Weight measured by digital electronic scale (Scaletronix) and stature on a stadiometer (Holtain). Age- and sex-specific Z-scores generated based on CDC 2000 growth charts so that DS and non-DS groups will be compared by the same reference. Body proportions and fat distribution measurements (sitting height, arm, waist and hip circumference, and skin fold thickness at triceps, biceps, subscapular, and supriliac sites) will be measured.

#### **5.1.7 Left Ventricular (LV) Mass**

LV mass will be measured by echocardiography, as described by the American Society of Echocardiography's guidelines. Per these guidelines the equation of Devereux et al will be used. LV Mass Index (LV mass/height2.7), has been used to normalize LV mass to body size. However, this index increases with decreasing height, which is not ideal for children with DS. Use of centile curves and z-scores is another strategy to account for

---

lean mass (LM), which may also be different in children with DS. We will measure LM by DXA and can thus normalize LV mass directly.

#### **5.1.7.1 Pregnancy Testing**

A urine pregnancy test will be performed for female subjects. A positive pregnancy result will be disclosed to the participant only. Pregnancy results will be disclosed to the parent/guardian if the subject gives the investigators permission. Subjects found to be pregnant during the visit will not be able to enroll in this study. The investigators will counsel the subject and guide them to seek the appropriate care.

#### **5.1.8 Safety Evaluation**

The study investigators will be responsible for safety monitoring. A routine needle stick or an IV line used for drawing blood may cause some discomfort (topical anesthetic cream will be available), bruising, and rarely fainting. Use of the anesthetic cream may cause an allergic reaction. Although high adiposity is possible in participants with BMI < 85th percentile and might contribute to abnormal glucose tolerance, we will limit the subjects undergoing OGTT 1) to minimize participant burden in this cohort of children with developmental disabilities, and 2) on the likelihood of finding cardiometabolic abnormalities. We confined our IR assessment to HOMA-IR rather than IVGTT or clamp studies--considered the gold standard for IR assessment-- in the spirit of sensitivity to these children with intellectual disabilities and their families. We will obtain interim time points within the OGTT to calculate ISI, a measure of whole body insulin sensitivity. This requires a minimum of 5 time points, necessitating the placement of a blood-drawing IV. Given the children's developmental disabilities, some children may not tolerate this procedure—in this subset only time points 0 and 120 will be drawn and ISI omitted from their analyses.

Participants will be fasting 12 hours prior to their study visit. This may cause hunger pangs, upset stomach, headache, or light-headedness. If the participant shows any signs of clinical instability or definitively decides to discontinue participation, the study visit will be ended. Possible side effects of the OGTT include temporary high or low blood sugar. A risk of the OGTT includes an upset stomach. Participants will be monitored by a nurse or doctor during the study procedures. Episodes of low blood glucose will be treated with oral or IV glucose when indicated.

During the study visit, if a participant is found to have any previously unknown medical conditions, they will be referred to their pediatrician for care.

This protocol also involves exposure to radiation from the DXA scans. However, this involves a very small radiation exposure, which is unlikely to cause any untoward effects to the participant. Being that the protocol may be unsafe to an unborn child, pregnancy is an exclusion criterion of the study.

The noninvasive measures of arterial stiffness and central pulse pressure are done via Pulse Wave Velocity and Pulse Wave Analysis. This poses little risk to the patient.

The patient will be notified of any clinically relevant abnormal test result(s) performed by CLIA certified labs, by mail and or by phone. Because of batching of samples, there may be a

---

significant time delay between the study visit and result notification. It will be recommended that results, especially abnormal results, be discussed by the guardian with the participant's primary care physician. In the case of study referrals by the primary care provider, the investigators may send study results via email, phone, and/or mail to the primary care physician directly. Studies performed by non CLIA labs will not be disclosed.

Any adverse events will be reported as per the study site policies.

## **6 STATISTICAL CONSIDERATIONS**

### **6.1 Data Analysis**

We will screen approximately 200 children with DS to enroll 155 evaluable children with DS. Approximately 50% will have CHD, which will be hemodynamically significant in approximately 50-75%. Subjects with minor, hemodynamically insignificant lesions (such as a small PDA) will be grouped with subjects without CHD.

Primary Aim: The primary aim is to compare the relationship between BMI-Z and cardiometabolic risk factors in youth with DS and matched controls. This relationship may be different in children with DS with and without CHD. In order to model the analyses appropriately, the primary outcome variables will be compared between children with DS with and without hemodynamically significant CHD. If the groups differ, subsequent analyses will include a dummy variable indicating presence/absence of hemodynamically significant CHD. Descriptive data analysis will summarize distributions of all risk factor measures (age, weight, BMI-Z, non-HDL-C, lipid levels, lipoprotein subclass particles, BP, HOMA-IR, ISI, inflammatory markers, adipokines, CPP, PWV, LV mass, gender, race, ethnicity, pubertal stage, pre-diabetes and diabetes status, physical activity). Subjects with DS will be compared to age-, sex-, race-, and BMI-Z matched controls, first by comparison of risk factor distributions by DS status. Next, we will fit separate regression models for each risk factor, with DS as the exposure of interest, adjusted for potential confounders, including pubertal stage, family history of CVD, dietary fat intake, and smoking history. Interaction terms among confounders will be used when data frequencies permit. Initial regressions will confirm the size and sign of associations of subject characteristics and CVD risk factors. Complementary analyses will implement propensity scores, using logistic regression to model DS as a function of observed covariates, and then will compare DS and non-DS children for each endpoint using weighted analyses. Weights will be calculated by the inverse of the fitted probability of DS. This method will standardize the comparisons of CVD risk factors by differences in observed characteristics of DS and non- DS children and thus will permit statements such as —If a sample of children otherwise comparable were alternatively DS and non-DS, what would be the differences in CVD risk factors? Finally, we will perform sensitivity analyses as to the potential impact on our results from unobserved potential confounders. Initial analyses will determine whether children with DS differ from their non-DS counterparts in terms of CVD risk factors and will become the basis for addressing the questions in the four sub-aims.

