### Setting/Participants:

The Children's Hospital of Philadelphia Clinical and Translational Research Center and Children's National Medical Center.

A total of 260 evaluable male and female subjects ages 10-20 years of any race or ethnic background will be recruited: 155 subjects with DS (with and without significant CHD) and 105 non-DS controls, matched for age, sex, race, ethnicity, and BMI-Z. Approximately 600 subjects will need to be screened in order to achieve this number of evaluable subjects.

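### A data-dependent rule for adding a significant-CHD dummy leaves open whether the adjusted DS main effect describes all DS or only DS without significant CHD (minor)

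*Combined protocol and SAP*

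**What the plan says.** The Abstract plans for "155 subjects with DS (with and without significant CHD) and 105 non-DS controls", and section 6.2 bases power on all 155. Of the DS children, "Approximately 50% will have CHD, which will be hemodynamically significant in approximately 50-75" per cent (section 6.1). Minor lesions are pooled with no CHD.

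The Primary Aim paragraph of section 6.1 motivates a CHD check: "This relationship may be different in children with DS with and without CHD". The relationship meant is that of BMI-Z with the risk factors. The check is that "the primary outcome variables will be compared between children with DS with and without hemodynamically significant CHD", followed by the rule: "If the groups differ, subsequent analyses will include a dummy variable indicating presence/absence of hemodynamically significant CHD".

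The main models come next: "Next, we will fit separate regression models for each risk factor, with DS as the exposure of interest, adjusted for potential confounders". A complementary propensity analysis "then will compare DS and non-DS children for each endpoint using weighted analyses". On interactions the paragraph says: "Interaction terms among confounders will be used when data frequencies permit". Section 6.1.1 separately adds DS by BMI-Z to each risk-factor model.

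**The concern.** The rule is a pre-test whose result changes the model, and three things about it are missing: the test, the threshold, and the outcomes that count. The text speaks of primary outcome variables in the plural, whereas section 6.2 names one primary measure, non-HDL-C.

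This differs from routine confounder adjustment. Significant CHD is a subset of DS, so putting it in the model changes the population that the DS coefficient describes. Section 6.3 intends to use confidence bounds to exclude differences that would matter clinically. Such bounds need a population fixed in advance, and here the data choose it.

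The rule also does not match its rationale. The worry is a different slope on BMI-Z, but the trigger compares outcome levels, the dummy as described moves only the intercept, and no CHD by BMI-Z term is named.

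**Working it through.** **Plan's own figure.** The rule carries no figure. The nearest one is the section 6.2 power above 0.85 for 0.35 SD with 155 vs 105. Taking the nonparametric test as Wilcoxon with relative efficiency 0.955, power = Φ(0.35 × √0.955 / √(1/155 + 1/105) − z) = Φ(2.706 − z). This is 0.856 with z = 1.645 (one-sided 0.05) and 0.772 with z = 1.960 (two-sided 0.05). The plan states neither alpha nor sidedness. That is a separate matter; here it means only that the pre-test level has to be assumed.

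**Inputs from the documents.** Significant CHD is 0.50 × 0.50 to 0.50 × 0.75 = 25% to 37.5% of 155, or 39 to 58 children. That leaves 116 to 97 DS children without it. The implied SD of non-HDL-C is 7 / 0.35 = 20 mg/dl (section 6.2).

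**Assumptions.** Two-sided 0.05 pre-test, equal SDs, controls coded 0 on the dummy. The CHD gap is unknown and is varied from 0 to 0.5 SD.

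**Meaning of the coefficient.** Let p be the CHD share within DS, 39/155 = 0.252 or 58/155 = 0.374.
- Without the dummy: b1 = mean(all DS) − mean(controls).
- With it: b1 = mean(DS without significant CHD) − mean(controls), and the all-DS effect is b1 + p × b2, where b2 is the CHD gap.
- The two meanings therefore differ by p × gap. For example, 0.252 × 0.35 × 20 = 1.8 mg/dl and 0.374 × 0.35 × 20 = 2.6 mg/dl.

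**Chance that the dummy enters.** This is about Φ(gap / √(1/m + 1/(155 − m)) − 1.96), plus a small opposite tail, with m = 39 or 58. The standard errors are 0.185 and 0.166 SD.

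**Coverage.** The two-step rule was simulated with 100,000 replicates per scenario, known SD and no covariates. The nominal 95% interval was scored against the all-DS effect. Each cell gives the values for 39 / 58 children with significant CHD.

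| CHD gap | Shift (mg/dl) | Dummy enters | Coverage of all-DS effect |
|---|---|---|---|
| 0 | 0 / 0 | 0.050 / 0.050 | 0.948 / 0.945 |
| 0.2 SD | 1.0 / 1.5 | 0.190 / 0.225 | 0.936 / 0.921 |
| 0.35 SD | 1.8 / 2.6 | 0.472 / 0.559 | 0.905 / 0.856 |
| 0.5 SD | 2.5 / 3.7 | 0.771 / 0.854 | 0.849 / 0.743 |

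A smaller simulation with covariates (4,000 runs, assumed slopes) gave 0.917-0.940, 0.858-0.918 and 0.745-0.865 at the three non-zero gaps. A fixed three-level model with a share-weighted all-DS contrast gave 0.949-0.952 without covariates and 0.944-0.956 with them.

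**Checks that limit the point.** Scored against the estimand of whichever model was fitted, coverage under the rule is 0.944-0.957. For the DS by BMI-Z interaction it is 0.945-0.954.

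**Cost of a needless dummy.** The SE ratio is √[(1/116 + 1/105) / (1/155 + 1/105)] = 1.066, or 1.114 with 97 in place of 116. The SE of the DS coefficient is thus 7-11% larger.

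**Power by target.** At 0.35 SD, two-sided 0.05 and efficiency 0.955, power is 0.77 for all DS (155) and 0.72 or 0.68 for DS without significant CHD (116 or 97).

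**The case against.** Much of the opposing case stands.

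- The primary objective is the BMI-Z relationship, tested by DS by BMI-Z, and the rule does not disturb that test. A reader might infer that the primary comparison is compromised; the simulated coverage does not support this.
- A reader might infer that the planned intervals are invalid. They are not: each has about nominal coverage for its own model's estimand. Coverage falls only when the interval is read as describing all DS. Whether the dummy is in a model will also be visible from its covariate list.
- A reader might infer that no all-DS estimate is planned. The comparison of distributions by DS status covers all DS, unadjusted. The propensity-weighted comparison, on its natural reading, does so with adjustment, although the plan does not say how it treats CHD. The gap is in the adjusted regressions.
- A reader might infer that coefficients would mean different things across outcomes even if CHD had no effect. At a zero gap the two meanings are numerically equal. In addition, the rule's reference to later analyses reads most naturally as applying to all models. Only the 7-11% SE cost remains in that case.
- A reader might take the sentence on interactions among confounders to exclude all others. Section 6.1.1 shows otherwise; what is missing is specifically a CHD by BMI-Z term.
- No CHD effect is documented, and the exclusions remove cyanotic and medically unstable CHD and pulmonary hypertension. Even at 0.5 SD the shift is at most 3.7 mg/dl, below the 10 mg/dl that section 6.2 treats as clinically relevant.
- The coding of controls is assumed. The Synopsis calls them healthy, but the exclusion criteria bar only certain kinds of CHD.

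What survives is that a stated pre-test, with no test, cut-off or defined trigger, selects the population behind the adjusted DS main effect.

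**Conclusion.** The point holds as a minor one, confined to the adjusted DS main effect when it is read as the effect for all DS. Its size depends on a CHD gap that the documents do not give: nothing at zero, a small effect up to 0.2 SD, and a material loss of all-DS coverage only at 0.35 SD and above, where the shift is 1.8-3.7 mg/dl against a 7 mg/dl design difference. At 0.35 SD the choice of model is close to a coin toss (0.47-0.56). All of these sizes rest on the assumed two-sided 0.05 pre-test, equal SDs, SD 20 mg/dl and controls coded 0. The missing specification itself needs none of them, and a fixed contrast removes the problem at almost no cost.

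**What to change.** Delete the conditional rule. For every outcome fit the same three-level group: control, DS without significant CHD, DS with significant CHD. Prespecify all DS versus control, weighted by the observed CHD share, as the main adjusted DS effect. If the team prefers DS without significant CHD as the target, name it in advance for every outcome and accept the lower power shown above. Report each DS subgroup versus controls, and the CHD contrast within DS, as secondary. State that the propensity-weighted comparison targets the same population.

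Optionally, show a CHD by BMI-Z term within DS as descriptive, since that is the plan's stated reason for the check.

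The cost is SAP wording, one degree of freedom and a few table rows, with no new data. Without covariates the share-weighted contrast equals the pooled comparison, so the gain is a fixed meaning plus subgroup estimates from one model, not extra power.

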#### **6.1.1 Aim 1a) BMI-Z scores and DS – CMR factors**

---

To analyze this aim, the statistical model noted above will be modified to include an interaction term between DS and BMI-Z score for each CVD risk factor. An important interaction term will reflect varying association of BMI-Z by disease status. Based on preliminary data we estimate 50% of subjects with DS will have BMI $\geq$ 85%ile and undergo an OGTT. We will compare prevalence of IGT or IFG and T2DM between groups. (Although DS is associated with increased risk for T1DM, this would most likely present acutely and have already been diagnosed if present.)

**6.1.2 Aim 1b) DXA-measured FM** This sub aim will make use of the model in Aim 1a. Inclusion of FM in explaining CMR factors in the model should offset any statistical interaction between BMI-Z and DS status.

**Aim 1c) PWV [and LV Mass]** Using the model outlined previously, we will add PWV as an indicator of end organ damage to assess additional information provided by PWV, especially with regard to the interaction of BMI-Z and CVD risk factor levels. This approach will be used for CPP and LV mass as well.

**6.1.3 Aim 1d) Discrimination ability of BMI-Z and other screening measures** This analysis will be confined to children with DS, and will require for each CVD risk factor the determination before analysis of a threshold of high versus low, in order to evaluate discrimination. With BMI-Z, and each risk factor taken individually, we shall estimate the c-statistic, a measure of discrimination representing the area under the ROC curve of the tradeoff of sensitivity and specificity, for each screening measure as a predictor of high vs. low risk. Finally, we shall compare the additional discriminatory power of adding one screening measure to an existing screening measure, such as WC to BMI-Z to determine whether an additional screen is worth the expense and time. These contrasts will be implemented using the methods outlined by Pepe and colleagues.

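### The plan expects the BMI-Z relationship to differ by CHD within DS, but a check on outcome levels and an intercept-only CHD dummy do not address a difference in slope

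*Combined protocol and SAP*

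**What the plan says.** Section 6.1 of the combined protocol and SAP frames the primary aim as a comparison of relationships: "The primary aim is to compare the relationship between BMI-Z and cardiometabolic risk factors in youth with DS and matched controls". It then raises CHD as a possible modifier of that relationship: "This relationship may be different in children with DS with and without CHD". The check that follows concerns the outcomes themselves: "the primary outcome variables will be compared between children with DS with and without hemodynamically significant CHD". The remedy is conditional on that check: "If the groups differ, subsequent analyses will include a dummy variable indicating presence/absence of hemodynamically significant CHD".

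Section 6.1.1 (Aim 1a) says that "the statistical model noted above will be modified to include an interaction term between DS and BMI-Z score for each CVD risk factor". Aim 1b reuses this model to ask whether fat mass accounts for the interaction, and Aim 1c adds PWV, CPP and LV mass to it.

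The only other provision for interactions is general: "Interaction terms among confounders will be used when data frequencies permit". The models are "adjusted for potential confounders, including pubertal stage, family history of CVD, dietary fat intake, and smoking history"; neither CHD nor BMI-Z is on that list. Section 6 contains no CHD x BMI-Z term, no CHD-specific slope and no analysis without the participants who have significant CHD.

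**The concern.** The stated worry is about a slope, but the check is about a level and the remedy is an intercept. Two DS subgroups can have similar mean outcomes and different BMI-Z slopes, and a level comparison is not designed to show that. If the check does fire, the dummy moves one subgroup's line up or down and leaves its slope tied to that of the other.

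At stake is how DS x BMI-Z is read in Aims 1a to 1c. If CHD changes the slope, part of that change is reported as a feature of DS. Aim 1b would then ask fat mass to explain an interaction that is partly due to CHD.

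**Working it through.** **The plan's own figure.** Section 6.2 claims power above 0.85 for a level difference of 0.35 SD with 155 and 105 participants. By normal approximation, 0.35 / sqrt(1/155 + 1/105) = 0.35 / 0.1264 = 2.77. One-sided at 0.05, power is Phi(2.77 - 1.645) = 0.87 (0.856 with the Wilcoxon efficiency of 0.955), which reproduces the claim. Two-sided, it is 0.79 (0.77), which does not; sidedness is not stated. Either way the figure concerns levels. The plan gives no power for DS x BMI-Z, so this figure neither supports nor weakens the point.

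**Share of DS with significant CHD (section 6.1).** About half have CHD, significant in 50 to 75% of these:
- 155 x 0.50 x 0.50 = 39, or 25%
- 155 x 0.50 x 0.75 = 58, or 37.5%

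**How much of a slope difference enters the coefficient.** Take a model with BMI-Z, DS, DS x BMI-Z and a CHD dummy. The DS slope is then the pooled within-subgroup slope. If the CHD slope differs from the non-CHD DS slope by d, the DS x BMI-Z coefficient moves by w x d, where w is the CHD share of the within-subgroup BMI-Z variation. With equal BMI-Z variances, w is 0.25 to 0.375. The dummy does not reduce this: in simulation, the plan's gated procedure and the always-included dummy gave estimates within 0.002 of each other (SD units).

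**Illustration in mg/dl.** Section 6.2 equates 0.35 SD with 7 mg/dl of non-HDL cholesterol, so SD = 7 / 0.35 = 20; this is used as the residual SD. The following are assumptions, because the documents give no slopes:
- BMI-Z SD of 1
- slope of 8 mg/dl per BMI-Z unit in controls and in DS without significant CHD
- slope of 2 in DS with significant CHD
- equal subgroup means

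Expected shift: 0.25 x (2 - 8) = -1.5 and 0.375 x (2 - 8) = -2.25.

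| Simulation result | 39 with CHD | 58 with CHD |
|---|---|---|
| Level check (rank-sum) fires | 4% | 5% |
| DS x BMI-Z shift, dummy included | -1.5 | -2.2 |
| Standard error, dummy included | 2.6 | 2.6 |
| Shift in standard errors | 0.6 | 0.9 |
| Rejection rate at nominal 5% | 0.08 | 0.14 |
| Shift with CHD x BMI-Z added | 0.0 | 0.0 |
| Standard error with CHD x BMI-Z | 2.7 | 2.8 |

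Shift and rejection rate are measured against the contrast of DS without significant CHD versus controls, which is zero by construction.

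The standard errors agree with the large-sample formula: 20 x sqrt(1/155 + 1/105) = 2.53, against 20 x sqrt(1/116 + 1/105) = 2.69 and 20 x sqrt(1/97 + 1/105) = 2.82. The simulated increase is 6% and 11%.

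**Does the level check catch slope differences?** Sometimes, indirectly. Section 6.1.1 expects half of DS participants at or above the 85th percentile, so median BMI-Z is near 1.04. With residual SD 1:
- Lines crossing near mean BMI-Z: the check fires in 5 to 8% of runs across slope differences of 0.2 to 0.5 SD per unit.
- Lines crossing at BMI-Z = 0: it fires in 19 to 21% of runs at 0.2 and 70 to 76% at 0.5.

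In the second case the remedy is still only an intercept, and the shift stays.

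**Power of CHD x BMI-Z itself.** At 0.35 SD per BMI-Z unit, power is 0.47 (25% CHD) or 0.56 (37.5% CHD).

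**The case against.** The strongest objection concerns the target. The Abstract recruits DS participants with and without significant CHD, and the Study Rationale and section 8.3.5 address clinicians who care for both. A slope averaged over the CHD mix is a proper answer for that population, and nowhere does the plan name DS without significant CHD versus controls as the target. This stands. A reader might infer that the planned coefficient is simply biased; the documents do not support that. It departs only from a contrast the plan never declares as its estimand.

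A reader might also infer that a CHD slope difference passes whole into DS x BMI-Z. It does not: the fraction is about a quarter to three-eighths. To cancel a true DS effect on the slope, the CHD difference would have to be 1/0.375 = 2.7 to 1/0.25 = 4 times as large and opposite in sign.

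Nor is the interaction the only answer to the primary aim. The synopsis hypothesis is about worse risk factors at a given BMI-Z, objective (a) compares risk factors between groups, and section 6.2 powers a level difference. For those questions a level check and an intercept term are relevant tools.

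The illustration is also unfavourable to the plan: the slope falls by three quarters, and equal means leave the check only its false-positive rate.

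Finally, the confounder list is open and interactions are allowed where data permit. That leaves room for CHD x BMI-Z but commits to nothing.

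**Conclusion.** The concern holds in a limited form. The plan raises a possible slope difference by CHD, then neither tests nor models one. The level check responds to slopes only by accident of where the lines cross, and the dummy cannot represent a slope difference. About 25 to 37.5% of any such difference enters DS x BMI-Z in Aims 1a to 1c. The coefficient is a valid average over the recruited CHD mix, but it varies with that mix and cannot be read as an effect of DS apart from CHD.

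The fraction rests on the CHD proportions in section 6.1 and on equal BMI-Z variances. The size in mg/dl rests on assumed slopes; the documents offer no evidence that a CHD slope difference exists or how large it is. In the illustration the shift is below one standard error. It is a gap worth closing before analysis, not a defect that invalidates the primary comparison.

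**What to change.** - State that the main estimate is the all-DS versus control DS x BMI-Z contrast, averaged over the recruited CHD mix, and report that mix.
- Replace the level-gated dummy with a prespecified companion model for Aims 1a to 1c containing significant CHD and CHD x BMI-Z. Fit it whatever the level comparison shows and whether or not the CHD term is significant.
- From the companion model, report the slope contrast of DS without significant CHD versus controls, and the CHD x BMI-Z estimate with its confidence interval.
- In Aim 1b, give the change in DS x BMI-Z after adding fat mass in both models.

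The cost is one extra interaction term, using a CHD classification the plan already makes. The standard error of the companion contrast is about 6 to 11% larger, because its DS slope rests on about 97 to 116 DS participants. The CHD x BMI-Z test has limited power (0.47 to 0.56 at 0.35 SD per unit), so it should be read as an estimate; a non-significant result is not evidence of equal slopes.

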**Study Objective(s)**

**Part 1:**

**Primary**

**To compare the relationship between BMI-Z score and cardiometabolic risk factors in youth with DS, and in age-, sex-, race-, ethnicity-, and BMI-Z score-matched controls.**

- a) Compare cardiometabolic risk factors [non-HDL cholesterol, lipoprotein subclass particles, blood pressure, insulin resistance (measured by HOMA-IR), insulin sensitivity index (ISI), glucose tolerance, inflammatory markers, and adipokines)] in adolescents with DS and in matched controls.
- b) Determine the extent to which adiposity (fat mass by DXA) explains this relationship in DS vs. controls.
- c) Assess cardiac end organ injury (pulse wave velocity (PWV) and left ventricular mass) in relationship to BMI-Z score in adolescents with DS and controls. Determine whether BMI-Z or other measures of adiposity (skin-fold thickness, waist circumference) better discriminates adolescents with DS at increased cardiometabolic risk.

**Hypothesis:** DS is associated with worse cardiometabolic risk factors for a given BMI-Z compared to controls. This difference arises at least in part, from increased adiposity.

---

---

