### Secondary

**To examine the relationship between obesity, lifestyle (physical activity, nutrition), body image, and quality of life in DS, and to explore barriers to maintaining a healthy weight in children with DS.**

- a) Compare the relationships between BMI-Z, and body image and quality of life in adolescents with DS with those of matched controls.
- b) Identify DS-specific barriers (i.e., nutrition, behavioral issues, body image, feeding behaviors, parental-and self-imposed activity restrictions) to maintaining a healthy lifestyle.

**Hypothesis:** Obesity negatively impacts body image and quality of life in adolescents with DS.

Obesity is associated with less physical activity.

Psychological, behavioral, physical conditions unique to DS impede maintenance of healthy lifestyle and weight.

---

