## **2.2 Secondary Aim**

The secondary objective is to examine the relationship between obesity, lifestyle (physical activity, nutrition), body image, and quality of life in DS, and to explore barriers to maintaining a healthy weight in children with DS.

a) Compare the relationships between BMI-Z, and body image and quality of life in adolescents with DS with those of matched controls.

b) Identify DS-specific barriers (i.e., nutrition, behavioral issues, body image, feeding behaviors, parental and self-imposed activity restrictions) to maintaining a healthy lifestyle.

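### The Down syndrome models adjust for dietary fat and smoking as confounders although both come after the exposure; report the Down syndrome difference without them first, then with them

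*Combined protocol and SAP*

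**What the plan says.** The analysis of the primary aim (section 6.1) has two steps. Matched subjects are compared "first by comparison of risk factor distributions by DS status". Then "we will fit separate regression models for each risk factor, with DS as the exposure of interest", and these models are "adjusted for potential confounders, including pubertal stage, family history of CVD, dietary fat intake, and smoking history". Section 6.1.1 extends that model with a DS by BMI-Z term for Aim 1a, and Aims 1b and 1c build on the result. A complementary propensity analysis works by "using logistic regression to model DS as a function of observed covariates"; those covariates are not listed.

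Three other places bear on this:

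- The primary hypothesis in the synopsis reads: "DS is associated with worse cardiometabolic risk factors for a given BMI-Z compared to controls".
- The secondary aim (section 2.2) is to "Identify DS-specific barriers (i.e., nutrition, behavioral issues, body image, feeding behaviors, parental and self-imposed activity restrictions) to maintaining a healthy lifestyle", and the matching synopsis hypothesis is "Psychological, behavioral, physical conditions unique to DS impede maintenance of healthy lifestyle and weight".
- Fat mass, which the primary hypothesis also treats as raised in DS, is not in the base model. It enters later, under Aim 1b (section 6.1.2), as an explanatory step: "Inclusion of FM in explaining CMR factors in the model should offset any statistical interaction between BMI-Z and DS status".

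The plan does not say whether the DS difference is meant to include or exclude whatever runs through diet.

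**The concern.** A confounder of the DS comparison has to be a cause, or share a cause, of having DS. What a 10- to 20-year-old eats or smokes cannot cause a congenital condition. Diet can be a consequence of it, and the secondary aim rests on that idea. On the plan's own premises, dietary fat may lie on a path from DS to lipids and the other risk factors. A model that holds it fixed then estimates the part of the difference that does not run through diet. The hypothesis asks about the difference at a given BMI-Z, not at a given BMI-Z and fat intake.

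Because Aims 1a to 1c inherit the adjusted model, no specified regression gives the DS coefficient or the DS by BMI-Z term without diet held fixed. This matters for use of the results. Section 6.3 intends to rule out clinically important differences from the confidence bounds, and says that a finding of lower risk could spare children screening. An absence of difference that holds only with diet held constant would not carry that conclusion.

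**Working it through.** **1. The plan's yardstick.** Section 6.2 gives power above 0.85 for 0.35 SD with 155 DS and 105 control subjects and a nonparametric comparison. It equates 0.35 SD with 7 mg/dl of non-HDL cholesterol, so the implied SD is 7 / 0.35 = 20 mg/dl. With Wilcoxon efficiency 0.955, the effective sizes are 148.0 and 100.3, and SE = sqrt(1/148.0 + 1/100.3) = 0.129 SD. Then 0.35 / 0.129 = 2.71, and power is:

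- Φ(2.71 − 1.645) = 0.856 at one-sided 5%, which reproduces the stated figure;
- Φ(2.71 − 1.96) = 0.772 at two-sided 5%, which does not.

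Section 6.2 states neither the level nor the sidedness. Both versions are carried below.

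**2. How the coefficients move.** Write fat intake as a·DS + g·BMI-Z + h·DS×BMI-Z, and let the outcome rise by b per unit of intake, everything in SD units. Adding intake to a linear model lowers the DS coefficient by a·b (at BMI-Z = 0), the BMI-Z slope by g·b and the interaction by h·b. Hence:

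- the DS coefficient moves only if a and b are both non-zero, and in either direction;
- the interaction moves only if the dietary gap between groups changes with BMI-Z;
- the BMI-Z slope moves if intake varies with BMI-Z, which is ordinary confounding of that slope.

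**3. Illustration for the DS coefficient.** The documents give neither a nor b, so both are assumed: a = ±0.25 to ±0.50 (the gap left after BMI-Z matching) and b = 0.1 to 0.3. The total difference is held at 0.35 SD. Power with diet in the model is Φ(d·√0.955 / SE − z), where

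- d = 0.35 − a·b
- SE = sqrt[(1 − b²)(1/105 + 1/155) / (1 − r²)]
- r² = a²p(1 − p) / [1 + a²p(1 − p)], with p = 155/260

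| a | b | a·b (SD) | mg/dl | share of 0.35 SD | d (SD) | power, one-sided | power, two-sided |
|---|---|---|---|---|---|---|---|
| 0.25 | 0.1 | 0.025 | 0.5 | 7% | 0.325 | 0.806 | 0.708 |
| 0.25 | 0.3 | 0.075 | 1.5 | 21% | 0.275 | 0.715 | 0.600 |
| 0.50 | 0.2 | 0.100 | 2.0 | 29% | 0.250 | 0.607 | 0.482 |
| 0.50 | 0.3 | 0.150 | 3.0 | 43% | 0.200 | 0.472 | 0.350 |
| −0.25 | 0.1 | −0.025 | −0.5 | −7% | 0.375 | 0.894 | 0.824 |
| −0.50 | 0.3 | −0.150 | −3.0 | −43% | 0.500 | 0.989 | 0.976 |

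A simulation of 1,000,000 subjects with a = 0.5 and b = 0.2 gave a DS coefficient of 0.350 without intake and 0.249 with it, as the identity predicts (0.35 − 0.10 = 0.25). If a or b is zero, nothing changes.

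**4. What cannot be computed.** No figure is offered for the interaction, because h is unknown and not bounded by anything in the documents. None is offered for smoking, because nothing in the documents links it to DS.

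**The case against.** The best defence is that the primary aim concerns the BMI-Z relationship in each group, not only a DS main effect. Diet and smoking can plausibly affect both BMI-Z and the risk factors, and for that slope they are ordinary confounders. Moreover, the comparison is already conditional on BMI-Z, which is itself affected by DS. If diet drives both BMI-Z and lipids, fixing BMI-Z opens a path through diet that adjusting for diet helps to close. This stands. A reader might infer that diet should be dropped from the Aim 1a model altogether; the documents do not support that, and the adjusted model should stay.

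Second, the matched comparison of distributions comes first, involves neither covariate, and appears to be what the power in section 6.2 rests on. So a diet-mediated difference in level would not vanish from view. This stands for the main difference. It does not help with the interaction, since a comparison of distributions has no DS by BMI-Z term.

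Third, a contrast with lifestyle held fixed is a legitimate question. Section 1.1 asks what is intrinsic to DS as against obesity, and section 6.1 describes the propensity contrast as one between otherwise comparable children. Controls also come partly through different recruitment channels, so diet may pick up family or selection differences. All of this argues for keeping an adjusted estimate, not for reporting it alone under the label of confounding.

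Fourth, pubertal stage is also measured after DS. That is fair: the plan should say how it regards that covariate too. It is not named among the barriers in section 2.2, so the internal tension is specific to diet.

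**Conclusion.** The concern holds in a limited form. Dietary fat is called a confounder in section 6.1, while section 2.2 and the synopsis treat nutrition as something DS affects, and the plan never says which DS difference it wants with respect to diet. The adjusted coefficient may therefore differ from the hypothesised difference at a given BMI-Z. Over the assumed grid the change is 0.5 to 3.0 mg/dl in either direction, or 7% to 43% of the 7 mg/dl target. These figures illustrate; they are not estimates, and they apply to the DS coefficient, not the interaction.

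Three stronger readings go beyond the documents. One is that part of the DS difference will certainly be adjusted away: if adolescents with DS eat less fat than controls and b is positive, adjustment enlarges it. Another is that smoking mediates the DS difference: only its timing is documented. The third is that the propensity model has the same fault: its covariates are not listed, so it may or may not.

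**What to change.** In section 6.1, for each outcome:

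1. Fit the DS model, and the Aim 1a model with the DS by BMI-Z term, without dietary fat and smoking. Name this as the estimate of the overall DS difference at a given BMI-Z.
2. Add the two covariates in a second model labelled as explanatory, in the way Aim 1b treats fat mass. Report both models and the change in the DS and interaction coefficients.
3. Retain the diet-adjusted Aim 1a model, and say that it also guards against dietary confounding of the BMI-Z slope.
4. List the propensity covariates. Run that analysis without dietary fat and smoking, with a version including them as a sensitivity analysis.

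No new data are needed. The cost is revised wording, one extra model per outcome, and two DS coefficients whose difference the report must explain.
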